5.7 Protocol compliance

This protocol will be strictly followed when implementing the study described. Planned deviations to the protocol are not allowed. When an accidental protocol deviation occurs, a record will be kept with the details of the deviation. This form will be submitted to the Chief Investigator and Sponsor immediately and the Chief investigator will keep this form in a locked cabinet at one of the offices of the University of Birmingham.

Constant deviations will be considered as serious breaches to the protocol. If this occurs, the Chief Investigator and sponsor will be informed in writing. Actions that have an effect on the safety or integrity of the participants or the safety of the trial will also be considered as serious breaches of protocol and if this occurs, the Sponsor and Chief Investigator will also be informed immediately.

5.8 Amendments

If at any stage an amendment is required, the Chief investigator will submit a written request to the Sponsor explaining any changes and their reasons. The Sponsor will review the request and will decide if it is a substantial amendment or a minor one. An amendment will be considered as substantial if it affects the safety or integrity of the participants, if it affects the scientific value of the study or if it is related to the conduct or management of the study. If a substantial amendment to the protocol or documents that supported the original application is required, a notice of amendment will be submitted to the review body from whom the original approval was received. If the amendment is non-substantial or minor, the appropriate form will also be submitted.

Each amendment will be included in the protocol. A document explaining the amendment and the reasons for it will be included in an appendix. The number of amendments done in a specific

version of the protocol will be stated in the last digit(s) of the protocol version number. For example, if the protocol version is 1.02, there will be two amendments done to that version.

6 Statistics and data analysis

6.1 Sample size calculation

We are aiming to recruit and test 30 participants. This number is based on similar studies that have assessed language development in children. Additionally, a formal size calculation was used. The calculation showed that in order to achieve a power of 0.8 with a medium effect size and an error probability of 0.05, (a minimum of) 24 participants that finish the study needed to be recruited. Considering that some participants might not finish the whole study and their data might be used, we will aim to recruit at least 30 participants.

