4.1.4. Consent

Parents/guardians will consent their willingness to take part in the study on behalf of their children. They will receive a detailed information sheet (see Appendix 1.2) and a verbal summary of the study by the researcher at the beginning of the initial session of the intervention programme. After this summary and before commencing the first training/testing, they will be asked to sign a consent form (see Appendix 1.3). This consent form states the activities the child will be introduced to and the duration. It emphasizes that participation is completely voluntary, that the parent/guardian can withdraw his/her child from the study at any time up to 1 month after the final session of the intervention programme and without giving any reason, and that this will not have any impact on any services provided by the Birmingham Community Healthcare NHS Foundation Trust in the future. Parents will also be informed that a follow up study will be conducted and will be asked to provide a separate signature if they agree to be contacted in the future to follow up on the progress of their child or not. With regards to the infants, a simple explanation (age appropriate) of the tasks will be provided to them. Afterwards, infants will be asked if they want to "play" with the researcher.

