4.1.5. Withdrawing criteria

Parents/guardians can fully withdraw their infants from the study at any stage and up to 1 month after the final session of the intervention programme without the need of providing any explanation. If this happens, all existing paper forms and electronic data related to the infants will be destroyed and their details in the participant database will be deleted. They will therefore not be contacted for any follow-up study. Parents/guardian can also decide not to take part in the follow-up study, either

by not signing the agreement for the follow-up contact on the initial consent form or by informing the researcher when being contacted to make arrangements for the follow-up testing. As with the intervention programme, parents/guardians can withdraw their children from the follow-up study at any time up to 1 month after the completion of the follow-up test. Parents will be informed that their decision to withdraw from the study will not affect any services provided to them by the Birmingham Community Healthcare NHS Foundation Trust.

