4.3.5. Higher-order generalization: At week 9, all infants will be assessed with four pairs of novel objects different to the ones used in previous sessions. The same procedure as the one for the first-order generalization will be followed and it will also last 8 minutes. This test will assess if infants have learned a general rule that one can extend novel labels based on shape similarities.

At the end of the study and independent of the type of intervention that the children took part in, parents/guardians will be asked about their thoughts about the development and implementation of the study, as well as about possible changes they made at home or any activities (such as music or dancing sessions) that their infants attended to while they were part of the study (see Appendix 1.6). Additionally, they will receive a Participant Debrief Sheet with more information about the specific intervention programme that their child received (see Appendix 1.7).

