6.3 Statistical analysis plan

Only data of infants that have completed the intervention will be fully analysed. Nevertheless, when possible, the total population assessed and the reason why certain participants did not finish the study (e.g. decided to withdraw, moved away, stopped attending) will be noted and reported in the study report. A full analysis of the data will be conducted once all data has been collected, which we anticipate to be after about 1 year of commencement of the study.

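### Section 6.1 makes no allowance for loss at the optional, separately consented one-year follow-up, so 24 infants for primary Objective C is not assured

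*Combined protocol and SAP*

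**What the plan says.** Section 3.1 lists three primary objectives. Objective C concerns language and cognition a year on, and is framed as a comparison with the specific-word intervention.

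Section 6.1 has a single calculation for the whole plan. It starts from 0.8 power, a medium effect and a 0.05 error probability, and concludes that "a minimum of) 24 participants that finish the study needed to be recruited". Because some children may not finish, "we will aim to recruit at least 30 participants". It names no endpoint, test, effect metric or dropout rate.

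The follow-up is a second consent stage. Under 4.1.4, parents "will be asked to provide a separate signature if they agree to be contacted in the future". Under 4.1.5, "Parents/guardian can also decide not to take part in the follow-up study", either by leaving that agreement unsigned or by refusing when contacted, and they may withdraw for up to a month after the follow-up test. Families who fully withdraw from the programme have their data and contact details removed and are not approached again.

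Section 6.3 states: "Only data of infants that have completed the intervention will be fully analysed". Section 6.3.2 repeats the completers-only restriction and sets follow-up language, visual spatial and working memory results against UK population means. It describes no comparison between the two arms at one year.

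**The concern.** The 20% allowance is the only protection for the required number, and it is not divided between the nine weekly sessions and the later follow-up. Objective C is exposed to both: loss during the programme, then non-agreement, refusal or loss of contact over the following year. A reader of 6.1 would take all three primary objectives to rest on 24 infants and 0.8 power. For Objective C neither figure has been worked out.

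What is at stake is how the one-year result is read. Section 6.3.2 wants to know whether children keep learning words afterwards or whether benefit is confined to the intervention period. A null result from around 20 children, read against a stated power of 0.8, could be given more weight than it can bear. A comparison with norms alone could not attribute any result to one intervention rather than the other.

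**Working it through.** **Inputs.** From 6.1: 24 finishers, at least 30 recruits, power 0.8, error probability 0.05, a medium effect. From 4.2: two randomised groups; the ratio is not given, so 1:1 is assumed. Loss rates at either stage are not in the documents, so a range is assumed.

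**1. The plan's own step from 24 to 30.** 24 / (1 − 0.20) = 30 exactly. The allowance is 30 − 24 = 6 infants, or 20% in total.

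**2. Can the 24 be reproduced?** Not from what is stated. For 0.8 power, 0.05 two-sided:

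- Two arms, d = 0.5, exact t: 64 per arm (51 one-sided).
- One sample, d = 0.5, exact t: 34 (27 one-sided; the one-sided normal approximation gives 24.7, hence 25).
- Repeated-measures group-by-time interaction, f = 0.25: 34 with 2 time points and correlation 0.5; 22 with 2 and 0.7; 24 with 3 and 0.6; 24 with 4 and 0.5.

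So 24 arises only under particular assumptions about repeated measures that 6.1 does not state. Those assumptions would not carry over to a follow-up language test given once.

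**3. Infants expected at follow-up from 30 recruits.** Expected number = 30 × (1 − programme loss) × (1 − follow-up loss). The chance of at least 24 is the upper binomial tail with n = 30 and that retention.

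| Programme loss | Follow-up loss | Retention | Expected | P(at least 24) |
|---|---|---|---|---|
| 5% | 5% | 0.9025 | 27.1 | 0.98 |
| 10% | 10% | 0.81 | 24.3 | 0.66 |
| 20% | 0% | 0.80 | 24.0 | 0.61 |
| 10% | 20% | 0.72 | 21.6 | 0.22 |
| 20% | 10% | 0.72 | 21.6 | 0.22 |
| 20% | 20% | 0.64 | 19.2 | 0.05 |

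To expect 24 at follow-up, recruits = 24 / retention: 24 / 0.81 gives 30, 24 / 0.72 gives 34, 24 / 0.64 gives 38.

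**4. Power and detectable difference, two-arm comparison.** Two-sided t-test at 0.05, equal arms, noncentral t.

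- At d = 0.5: power 0.22 with 24 infants, 0.17 with 18.
- Difference detectable with 0.8 power: 1.20 SD with 24, 1.27 SD with 21.6, 1.36 SD with 19.2.

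**5. Comparison with a norm, one group.** At d = 0.5, two-sided: power 0.65 with 24 infants and 0.54 with 19. Pooling all infants against UK norms does not reach 0.8 at d = 0.5 either.

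**The case against.** A reader might infer that the nine-session programme uses up the whole allowance and that Objective C therefore cannot reach 24. The documents do not support that. No programme dropout rate is given. Section 6.1 speaks of not finishing the whole study, which can include the follow-up, since 4.2 lists it under study design. On that reading the same six infants must cover both stages, and 24 remains reachable if total loss is 20% or less. Thirty is also a floor: five infants a month for up to 12 months (6.2) could yield 5 × 12 = 60. Other wording points towards a programme-only allowance. Section 4.3.5 uses "At the end of the study and independent of the type of intervention" for the last programme session, and 6.3 defines the analysed set by completing the intervention. Neither reading is settled.

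A reader might also infer that Objective C starts at 0.8 power and loses some points through attrition. That would hold only for an effect of about 1.20 SD, obtained by working backwards from 24. The plan says medium and ties the 0.8 to no endpoint.

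Finally, the statement about benefit lasting only while the programmes run is one side of a question in 6.3.2, not a rule triggered by a non-significant test. Against UK norms, a non-significant gap might instead be read as catching up. This is a reason to specify the comparison, not a reason to leave it.

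What stands after these points: there is one undivided allowance, nothing explicit for the optional follow-up, and no between-arm analysis of an objective defined between arms.

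**Conclusion.** The concern holds as a lack of assurance, not as an impossibility. Section 6.1 provides no explicit allowance for loss at the follow-up that carries a primary objective. With 20% programme loss and 10% to 20% follow-up loss, about 22 to 19 infants remain; with 10% at each stage, about 24. These rates are assumptions, as is a recruitment of exactly 30.

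The larger weakness is that 24 and 0.8 are linked to no endpoint or test. For a two-arm comparison at d = 0.5, power is about 0.22 even with full retention of 24, so better retention alone would not make Objective C adequately powered. The norm-only analysis in 6.3.2 leaves the stated comparison unanswered at any sample size. The plan should be amended on these points; all are inexpensive.

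**What to change.** 1. **Section 6.1.** Name the endpoint, test and effect metric to which 24 and 0.8 apply. Do not claim 0.8 for Objective C or for all outcomes measured by week 9. State expected programme and follow-up retention separately. For Objective C, give the expected follow-up number and detectable difference over a stated uptake range (for example, with 24 programme completers, 90% to 80% uptake leaves 21.6 to 19.2 infants and a two-arm detectable difference of 1.27 to 1.36 SD).
2. **Section 6.3.2.** Estimate the one-year difference between arms with its 95% confidence interval, alongside the comparison with UK norms. State that a non-significant result will not be read as showing that benefit has stopped.
3. **Sections 4.4, 6.3 and 6.3.2.** Invite to follow-up every randomised infant whose parent agreed to be contacted and has not withdrawn, including those who stopped attending sessions. Change the completers-only wording so that these infants are analysed in the arm to which they were randomised. Without that second change the extra visits would add nothing to the analysis.

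At 80% uptake, inviting all 30 gives at most 0.80 × 30 = 24, against 0.80 × 24 = 19.2 from completers alone. The gain is smaller if families withdraw or if non-completers respond less often, so it recovers part of the shortfall. The cost is wording, up to about five extra follow-up visits (24 − 19.2 = 4.8) and a less favourable stated power for Objective C.

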6.2 Planned recruitment rate

Recruitment rate was discussed between the Chief Investigator, the Main Researcher and a Speech and Language Therapist of the Birmingham Community Healthcare NHS Foundation Trust.

Considering the number of Late Talkers that the Trust assesses each month that fall into the target group of this project, it is expected to recruit an average of five infants per month and all participants within 12 months.

6.3 Statistical analysis plan

Only data of infants that have completed the intervention will be fully analysed. Nevertheless, when possible, the total population assessed and the reason why certain participants did not finish the study (e.g. decided to withdraw, moved away, stopped attending) will be noted and reported in the study report. A full analysis of the data will be conducted once all data has been collected, which we anticipate to be after about 1 year of commencement of the study.

6.3.1 Summary of baseline data

From the total number of assessments and tasks, results from five of them will be used as baseline data or descriptive statistics. These five assessments are: Vocabulary checklist, Socioeconomic and general development questionnaire, attention task, sorting task, initial working memory assessment, and initial visual spatial abilities assessment. The description of the variables analysed on each assessment and how they will be reported is as follows.

- A. Vocabulary assessment: Parents will fill out this checklist before (and after) the intervention and the total number of words that the infant understands and the total number of words they

produce will be registered as continuous variables and will be considered as the baseline language ability before the intervention programme.

- B. Socioeconomic and general development questionnaire: This questionnaire will provide information regarding general child development, language delay family history, and family status. A number of different types of variables will be collected: nominal variables (e.g. occupation) and ordinal variables (e.g. infant's order of birth). These variables will be used for descriptive statistics. They are potentially interesting as predictor variables, but the sample size is likely too small to draw any strong conclusions.
- C. Attention measure: With this measure, we will assess the fixation duration (number of milliseconds an infant looks) towards a novel object that is moved. The object will be moved for 25 seconds (25000 ms) and the infant's total looking time towards the screen will be registered. This variable will be registered as a continuous variable and used as a predictor of the primary outcome measures.
- D. Sorting task: This will be registered as a categorical variable. Infants will sort objects and depending on their sorting tendency they will be assigned to one of four categories: preference for shape, preference for colour, preference for texture, no preference. This variable will be used as a predictor of the primary outcome measures.
- E. Working memory and visual spatial abilities: Using the Wechsler Preschool & Primary Scale of Intelligence - Fourth UK Edition (WPPSI-IV UK), infants working memory and spatial abilities will be assessed and compared to a standardized mean of the UK infant population. These variables will be used to assess in a non-verbal manner the participant's cognitive skills to rule out any possible cognitive delay.

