3.2. Secondary objectives

As a secondary objective, the study will investigate whether some children are more receptive to the shape bias intervention programme than others. More specifically, we will:

- D. Assess whether the success of teaching Late Talkers a shape bias for noun extension is related to their sensitivity to object shape similarities.
- E. Assess whether the success of teaching Late Talkers a shape bias for noun extension is related to their ability of sustain their attention to novel objects that are presented to them.

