3.4. Secondary outcome measures

Objective D), i.e. whether children are more receptive to the shape bias intervention if they are sensitive to shape similarities, will be assessed by relating children's ability to sort objects by shape before the intervention and their ability to extend object labels by shape after the intervention.

Objective E), i.e. whether children' are more receptive to the shape bias intervention if they can sustain their attention to novel objects, will be assessed by relating children's sustained attention during the presentation of a video showing a person presenting and moving novel objects before the intervention, their attention to the novel objects during the intervention, and their ability to extend object labels by shape after the intervention.

4. Method

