4.3. Tests and procedure of intervention programme

4.3.1. Vocabulary and developmental assessments. At session 1, parents/guardians will fill in a socioeconomic and general development questionnaire (see Appendix 1.5). The

information provided in this questionnaire will double-check the inclusion/exclusion criteria. It will also be used to check whether the intervention was only successful in a sub-group of the infants (e.g. those without a family history of language problems). In the first and last session, parents/guardians will also be asked to fill in the UK-CDI Words and Gestures questionnaire, a vocabulary checklist of words and phrases that infants might know and use (Alcock, Meints, & Rowland, 2017; see Appendix 1.4). This will allow us to compare language development during the intervention programme between the two intervention groups.

4.3.2. Initial cognitive assessments: The initial cognitive assessments will be presented during the first two sessions. During week 1, infants will be assessed with a shape sorting task and an attention task. The sorting task will last no more than 5 minutes and will be used to assess if before the training programme, infants are sensitive to the shape of objects and can group objects by shape. Infants will be presented with 16 novel objects differing in shape, colour and texture and asked to sort them into groups. How to sort (namely by shape) will be shown to them with the means of examples. The attention task will last 3 minutes and will assess infants' joint and sustained attention. This will be achieved by monitoring their eye movements during the presentation of five short video clips (35 seconds each) of a person looking at and moving unusual novel objects. For this task, participants will sit on their parent/guardian's lap in front of a computer screen. Eye movement will be monitored with a remote eye tracker (see Figure 2). The parent will wear blacked-out glasses so that their behaviour cannot affect the infants' eye gazes.

At week 2, infants' visual spatial abilities and working memory will be assessed using the Wechsler Preschool & Primary Scale of Intelligence - Fourth UK Edition (WPPSI-IV UK). This test will last about 20 minutes and will be used to rule out any potential cognitive delay.

Figure 2. Attention task. Infants will watch five short videos and eye movements will be monitored with a remote eye tracker.

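### Section 6.3.1 C defines the pre-test attention predictor as fixation on the moving object but registers looking time to the whole screen; it should name the object measure.

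*Combined protocol and SAP*

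**What the plan says.** Section 6.3.1 C describes the attention measure in consecutive sentences. It opens with the construct: "we will assess the fixation duration (number of milliseconds an infant looks) towards a novel object that is moved". It then states 25 seconds (25000 ms) of object movement and, in the same sentence, gives the recording rule: the infant's "total looking time towards the screen will be registered". It closes with the use: "This variable will be registered as a continuous variable and used as a predictor of the primary outcome measures".

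Section 4.3.2 describes the stimulus as "five short video clips (35 seconds each) of a person looking at and moving unusual novel objects", with gaze followed by a remote eye tracker, and gives the aim of the task as joint as well as sustained attention.

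Objective E (section 3.2) concerns the child's "ability of sustain their attention to novel objects that are presented to them". Section 3.4 asks whether children respond better to shape training "if they can sustain their attention to novel objects". It uses two measures for this: sustained attention during the pre-intervention video, and attention to the objects during training. Section 6.3.2 enters both in the mixed-effect models, and section 6.3.3 refers back to those models.

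**The concern.** The construct named in the first sentence and the quantity registered in the second differ whenever an infant looks at something on the screen other than the object. The clips make that likely, because a person is in view, handling and looking at the object. Read literally, the variable carried into the models is screen time.

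At stake is what the pre-test attention term can show. Section 6.3.2 intends to learn whether only infants who attend to the novel items can acquire a shape bias. A score that gives equal credit for watching the person answers a broader question about general attention to a video. Leaving two scorings open also means that the choice between them could be made after the outcome data have been seen.

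**Working it through.** The plan states no statistical figure for this point, so the check is a comparison of texts, a timing check and a small scoring example.

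**Definitions side by side**

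| Place | Target of attention |
|---|---|
| 3.2, Objective E | Novel objects |
| 3.4, pre-test part | The video of a person moving novel objects; no area of interest given |
| 3.4, in-training part | Novel objects |
| 6.3.1 C, first sentence | The moved novel object |
| 6.3.1 C, second sentence | The screen |
| 6.3.2, stated aim | Novel items |

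Only the recording rule names the screen. No area of interest is defined anywhere, and no rule converts screen time into object fixation.

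**Timing** (sections 4.3.2 and 6.3.1 C)

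- 25 s × 1000 = 25,000 ms, as stated.
- 5 clips × 35 s = 175 s, and 175 / 60 = 2.9 minutes, which agrees with the stated 3-minute task.
- Assuming that the 25 s of movement is per clip, movement takes 25 / 35 = 71% of each clip, or 5 × 25 = 125 s of 175 s.
- The 25 s stands in the same sentence as the looking time, so it is the natural counting window, but the text does not say so outright. Nor does it say how the five clips are combined.

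**Scoring example** (hypothetical infants, one 25 s movement window)

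| Infant | Screen time | Object fixation | Object fixation / tracked time |
|---|---|---|---|
| A: on screen for 25 s, 20 s of it on the object | 25,000 ms | 20,000 ms | 20/25 = 80% |
| B: 3 s on the object, then turns away | 3,000 ms | 3,000 ms | 3/3 = 100% |
| C: watches the person for all 25 s | 25,000 ms | 0 ms | 0/25 = 0% |

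The last column assumes that the tracker has no valid gaze once the infant turns away.

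Screen time cannot separate A from C, and it ranks C above B although C never looked at the object. Object fixation in milliseconds gives A, then B, then C. The share of tracked time puts B first, so it does not measure sustained attention either. The example shows that the measures can order infants differently; it does not show how often they would.

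**The case against.** The strongest reply is that the text is inconsistent rather than settled on screen time. The opening sentence of 6.3.1 C names object fixation, and an eye tracker is provided that could deliver it. A reader might infer that Objective E is tested with the wrong variable, but the documents do not support that. They give two definitions, and Objective E also draws on attention during training, which the disputed sentence leaves untouched. That in-training measure has no stated scoring, however, so it does not make up for an unclear pre-test one.

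Section 3.4 describes the pre-test component as sustained attention during the video, and section 4.3.2 includes joint attention among the aims. Looking at the screen is a reasonable, if less specific, index of the first, and looks at the person are not plainly irrelevant to the second. This stands as a reason to keep screen time as a secondary description. It does not make screen time the better predictor for a question about novel objects.

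A reader might also infer a definite loss of power. With an assumed true correlation of 0.5 between object attention and noun extension, and an assumed correlation of 0.5 to 0.8 between screen time and object fixation, the observable correlation would be 0.5 × 0.5 = 0.25 to 0.5 × 0.8 = 0.40. Neither input is in the documents. The product rule holds only if screen time relates to noun extension solely through object fixation; if general attentiveness matters too, the association need not shrink. The plan also uses mixed models with several factors, not a single correlation.

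Nor does it follow that 5 × (35 − 25) = 50 s of 175 s (29%) of the recorded looking falls outside object movement. That needs a full-clip window, which 6.3.1 C does not suggest.

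**Conclusion.** Section 6.3.1 C contradicts itself, and its literal recording rule yields a less specific measure of attention to novel objects than its own opening sentence promises. This is worth correcting before any gaze data are scored.

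The scope is narrow: the pre-test attention predictor in 6.3.2 and 6.3.3. A reader might infer that the comparison of vocabulary growth between the interventions is compromised. It is not: the measure is taken before the intervention, and noise in a baseline predictor does not bias a randomised comparison.

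The size of the effect on the attention result cannot be computed from the documents, because nothing in them says how much on-screen looking goes to the person or background. The conclusion rests on the clips showing a person as well as the object, as section 4.3.2 states. The 25 s window per clip is an assumption that the revised text should confirm.

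**What to change.** In section 6.3.1 C, replace the recording rule with a single definition:

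- **Variable:** total fixation time, in milliseconds, inside a moving area of interest around the object.
- **Window:** the 25 seconds of object movement, stating that this is per clip if so.
- **Combination:** the average over clips with adequate tracking. Fix the criterion for adequate tracking in advance and base it on tracker failure, so that clips are not dropped because the infant looked away.
- **No division by validly tracked time:** looking away must lower the score, and the plan's own unit is milliseconds.

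Name this variable as the pre-test attention predictor in sections 6.3.2 and 6.3.3. Keep total screen-looking time as a descriptive or sensitivity measure of general attention, and report tracking loss separately.

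The cost is a change of wording and the drawing of areas of interest that follow the object in five clips. No new data are needed, and nothing changes for the families.

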6.3.3 Secondary outcomes analysis

As mentioned before, a mixed effect model analysis will be conducted and two of the factors introduced in this model will be the attention measure and the sorting task. With this, we will assess the role of attention and sorting abilities in word learning with the objective of knowing if only infants with certain attention patterns and/or infants that are sensitive to shape similarities can develop a shape bias.

7 Data management

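### The sorting task is scored as a four-class preference, which does not match Objective D's ability to sort by shape, discards graded information and uses 2 more degrees of freedom than a single shape score

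*Combined protocol and SAP*

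**What the plan says.** Section 4.3.2 describes the task: "Infants will be presented with 16 novel objects differing in shape, colour and texture and asked to sort them into groups". It then adds: "How to sort (namely by shape) will be shown to them with the means of examples". The stated purpose is to see whether, before training, "infants are sensitive to the shape of objects and can group objects by shape".

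Section 3.4 sets out how Objective D is to be examined: "relating children's ability to sort objects by shape before the intervention and their ability to extend object labels by shape after the intervention".

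Section 6.3.1 D registers the result as categorical, with four levels: "preference for shape, preference for colour, preference for texture, no preference". The variable is to serve as a predictor of the primary outcomes. Section 6.3.2 lists it among the main model factors, with baseline vocabulary, intervention type and two attention measures (before and during training). Section 6.3.3 gives the analysis for Objective D: "two of the factors introduced in this model will be the attention measure and the sorting task".

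The plan gives no rule for assigning a child to a class, no coding of the factor, no graded score and no power for Objective D.

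**The concern.** The objective, the task and the scoring do not describe the same quantity. The objective and the task are about whether a child can group by shape. The score records which property the child favours. Because sorting by shape has just been demonstrated, a recorded preference is not a clean preference. For Objective D, the colour, texture and no-preference classes all mean that the child did not sort by shape.

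Two statistical costs follow. Any gradation across 16 objects is lost when a child is put in a single class. A four-level factor also takes 3 degrees of freedom in a model fitted to about 24 to 30 children, or about 12 to 15 if Objective D is examined in the shape arm alone. At stake is the precision of the only analysis given for Objective D. The missing assignment rule also leaves a choice that could be made after the data are seen.

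The plan is more cautious with its other predictors. Section 6.3.1 B doubts that the sample can support strong conclusions from questionnaire variables, and 6.3.1 C keeps attention continuous.

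**Working it through.** **The plan's own figure.** Section 6.1 gives 24 completers (30 recruited) for power 0.8, a medium effect and error probability 0.05. It names neither the test nor the effect metric, so 24 cannot be derived from the stated inputs alone. One set of inputs that gives it is a two-group repeated-measures interaction with f = 0.25, four measurements and correlation 0.5 (power 0.816), but none of these is stated. The figure is not a power statement for Objective D.

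**Inputs.**
- 16 objects and the shape demonstration: section 4.3.2.
- Four classes, so 3 df: section 6.3.1 D.
- Four other named terms (baseline words, arm, two attention measures): section 6.3.2. Within the shape arm this becomes three.
- N = 24 to 30: section 6.1.
- Assumed: 1:1 allocation (ratio not stated), giving 12 to 15 per arm; f² of 0.0625, 0.15 and 0.35; one outcome score per child, so that the mixed model is approximated by a fixed-effects F test; all four classes occupied.

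**Step 1: degrees-of-freedom cost alone.** Power = P(F′ > F₀.₉₅), where F′ is noncentral F with u numerator df, v = N − u − (other terms) − 1, and noncentrality λ = f²·N.

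For f² = 0.15 and N = 24, λ = 0.15 × 24 = 3.6.
- Single score: u = 1, v = 24 − 1 − 4 − 1 = 18, critical F = 4.41, power 0.435.
- Four classes: u = 3, v = 24 − 3 − 4 − 1 = 16, critical F = 3.24, power 0.261.
- Ratio: 0.261 / 0.435 = 0.60.

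| f² | N | 1 df | 3 df | share kept |
|---|---|---|---|---|
| 0.0625 | 24 | 0.213 | 0.129 | 0.61 |
| 0.0625 | 30 | 0.260 | 0.159 | 0.61 |
| 0.15 | 24 | 0.435 | 0.261 | 0.60 |
| 0.15 | 30 | 0.530 | 0.340 | 0.64 |
| 0.35 | 24 | 0.783 | 0.561 | 0.72 |
| 0.35 | 30 | 0.875 | 0.700 | 0.80 |
| 0.15 | 12 (shape arm) | 0.214 | 0.110 | 0.51 |
| 0.15 | 15 (shape arm) | 0.274 | 0.148 | 0.54 |

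At N = 24 to 30 the relative loss is therefore about 20-40%. For f² = 0.15, 80% power needs 55 children with 1 df and 77 with 3 df.

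**Step 2: adding the information lost by classifying.** This needs an assumed sorting distribution. Shape count is Binomial(16, logistic(−0.6 + z)), with z standard normal. The remaining objects are split among the other three outcomes by a child-specific symmetric Dirichlet. The class is the largest count. The true correlation with noun extension is 0.5, the test is two-sided at 5%, and n = 24.

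| Assumed relation | Count, 1 df | Four classes | Shape v other, 1 df |
|---|---|---|---|
| Linear in sorting ability | 56-59% | 23-26% | 39% |
| Depends only on being a shape sorter | 54-57% | 56-58% | 77-79% |

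A second simulation of the linear case used a different sorting distribution and required at least 9 of 16 objects for a preference. Four-class power was 34-58% of count power at n = 15 to 30.

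**Step 3: effect on the arm comparison.** If the sorting factor explains nothing, the 2 extra df multiply the width of the arm-effect interval by about √(19/17) × t₁₆/t₁₈ = 1.057 × (2.120/2.101) = 1.07 at N = 24. At N = 30 the factor is √(25/23) × t₂₂/t₂₄ = 1.05. The interval widens by about 5-7%.

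**The case against.** The strongest objection is that the large simulated gap comes from assuming a linear relation, which favours a linear count. Sections 6.3.2 and 6.3.3 ask whether only children sensitive to shape similarity can acquire the bias, which is closer to a threshold. Under a threshold the count has no advantage over the four classes. This stands, and the linear figures should not be quoted without their assumption. It does not rescue the four-class factor, because under a threshold a binary shape term clearly beats it.

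It is also fair to say that a consistent colour sorter differs from a child who did not understand the task, and a single shape measure merges them. That is a real but small loss for an objective about sorting by shape.

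Stronger readings that a reader might infer are not supported:
- *Most of the power is lost.* This holds only under particular assumptions about the relation, the sorting distribution and the cut-off, none of which the documents give.
- *The cost is 3 degrees of freedom.* A score uses 1 itself, so the extra cost is 2.
- *Empty classes are likely in the full sample.* With the largest-count rule, an empty class arises in about 3% of simulated trials at n = 24 and 29% at n = 12. A stricter cut-off gives 30% and 67%. The plan states no cut-off.
- *Object placements are recorded anyway.* Section 6.3.1 D assigns a class from sorting tendency, which does not require object-level records.

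**Conclusion.** The point holds as a mismatch between objective, task and scoring, with a moderate and avoidable loss of efficiency. Relative to one shape score, the four-class factor costs 2 extra degrees of freedom. That removes about 20-40% of the power at N = 24 to 30 for equal explained variance, and about half or more if the relation is linear. If only shape-sorter status matters, the count and the four classes are about equal and a binary term is better. Across the cases examined, a 1-df shape measure is never materially worse.

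Two limits apply. Sample size is the main constraint: for f² = 0.15 even a 1-df score has power of only 0.44 to 0.53 with 24 to 30 children, so rescoring does not make Objective D adequately powered. The effect on the intervention comparison is small, a 5-7% wider interval. The conclusion rests on the assumed f² values, 1:1 allocation, the fixed-effects approximation and, for the linear and threshold figures, the simulated sorting distribution.

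**What to change.** In section 6.3.1 D, replace the four-class predictor with one 1-df shape-sorting measure, chosen before data are seen:
- the number of the 16 objects grouped by shape, with a one-line definition of what counts as grouped by shape; or
- if placements are not recorded, shape preference versus all other classes, with the assignment rule stated.

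In section 6.3.3, test this measure for Objective D within the shape arm or as a measure-by-arm interaction. The interaction needs 1 df, against (4 − 1) × (2 − 1) = 3 for four classes. Keep the four classes as a descriptive table.

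The cost is analysis wording and, for the count, recording where each object is placed. No extra visit, task or child is needed. The small downside is that colour and texture sorters are merged with no-preference children in the model; the descriptive table still shows them.
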